5.2.5 Serious Adverse Reaction

An adverse event or suspected adverse reaction is considered serious if, in the view of either the investigator or sponsor, it results in any of the following outcomes:

- Death
- Life-threatening adverse event
- Inpatient hospitalization or prolongation of existing hospitalization
- A persistent or significant incapacity or substantial disruption of the ability to conduct normal life function
- Congenital anomaly/birth defect

Important medical events that may not result in death, are life-threatening, or require hospitalization may be considered serious when, based upon appropriate medical judgment, they may jeopardize the patient or subject and may require medical or surgical intervention to prevent one of the outcomes listed in this definition. Examples of such medical events include allergic bronchospasm requiring intensive treatment in an emergency room or at home, blood dyscrasias or convulsions that do not result in inpatient hospitalization, or the development of drug dependency or drug abuse.

5.2.6 Life-threatening Adverse Events

An adverse event or suspected adverse reaction is considered life-threatening if, in the view of either the investigator or sponsor, its occurrence places the patient or subject at immediate risk of death. It does not include an adverse event or suspected adverse reaction that, had it occurred in a more severe form, might have caused death.

5.3 REPORTING ADVERSE EVENTS

Reporting of serious adverse events will follow the current requirements of the Committee on Human Research (CHR). Specifically, the following will be reported within five (5) working days of the PI's awareness, in writing:

- All serious adverse events associated with the study procedures and/or
- Any incidents or problems involving the conduct of the study or patient participation, including problems with the recruitment and/or consent process. The Principal Investigator will provide a discussion of such events to the CHR on an annual basis during study renewal.
- Any incidents or questionable adverse events are discussed at the weekly staff meetings with the PI.

The standard adverse event grading scale will be used to report any potential adverse events from phlebotomy, study drug, or other study procedures:

- 1. Mild AE: did not require treatment
- 2. Moderate AE: resolved with treatment
- 3. Severe AE: resulted in inability to carry on normal activities and required professional medical attention
- 4. Life-threatening or disabling AE
- 5. Fatal AE

The supervising study physician will be notified of all grades 2 through 5 AEs. Additionally, [name] will be notified of all grades 4 and 5 AEs.

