5 ADVERSE EVENTS & PROTOCOL DEVIATIONS

5.1 SAFETY MONITORING

During the outpatient stay, subjects will be monitored by the Clinical Research Coordinator and 5B staff who will directly contact the study physician in case of any subsequent adverse events. If the subjects experience serious adverse effects, the research staff will evaluate this with them and decide if they should be withdrawn from this study.

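### Adverse event grades 1 to 3 in section 5.3 overlap and leave gaps, so an incapacitating event that needs no treatment can be recorded as Mild and fall outside that section's physician-notification rule

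*Combined protocol and SAP*

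**What the plan says.** Section 5.3 sets out a five-point scale for adverse events arising from phlebotomy, study drug or other study procedures. The entries that matter here are:

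- Grade 1: "Mild AE: did not require treatment".
- Grade 2: "Moderate AE: resolved with treatment".
- Grade 3: "Severe AE: resulted in inability to carry on normal activities and required professional medical attention".
- Grade 4: "Life-threatening or disabling AE".

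Grade 5 is a fatal event. The same section ties notification to the grade: "The supervising study physician will be notified of all grades 2 through 5 AEs".

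Section 5.1 covers the outpatient stay. It says participants are monitored by the coordinator and ward staff, "who will directly contact the study physician in case of any subsequent adverse events". It gives no grade threshold.

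Seriousness is defined separately, in 5.2.5, and does not depend on grade.

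**The concern.** A severity scale should order events by how badly the participant was affected. Grades 1 and 2 contain no such criterion: one asks whether treatment was needed, the other whether treatment worked. Function first appears at grade 3, where it is joined by an "and" condition on professional attention. A participant who cannot carry on for a time after a session, but recovers without needing treatment, therefore meets the definition of Mild. A slight headache that resolves with a tablet meets the definition of Moderate.

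Two things are at stake. Safety of vaped cannabis, alone and with nicotine, is part of the research question in 1.2. With 14 participants, a few events graded differently by different staff could change the safety description. In addition, the 5.3 notification rule takes the grade as its input, so an ambiguous or missing grade makes it unclear whether the rule applies.

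**Working it through.** The plan gives no figure to reproduce. The check applies the definitions in 5.3 literally to every combination of the attributes they use, for events that are not life-threatening, disabling or fatal.

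**Inputs, all from 5.3**

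- Treatment: not required; required and resolved with it; required and not resolved with it (3 states).
- Inability to carry on normal activities: no or yes (2 states).
- Professional medical attention required: no or yes (2 states).

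Number of profiles = 3 × 2 × 2 = 12.

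**Rules applied**

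- Grade 1 if treatment was not required.
- Grade 2 if the event resolved with treatment.
- Grade 3 if incapacity = yes and attention = yes.

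| Treatment | Able, no attention | Able, attention | Unable, no attention | Unable, attention |
|---|---|---|---|---|
| Not required | 1 | 1 | 1 | 1 and 3 |
| Resolved with it | 2 | 2 | 2 | 2 and 3 |
| Not resolved with it | none | none | none | 3 |

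**Grades per profile**

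- Exactly one grade: 3 + 3 + 1 = 7.
- Two grades: 1 + 1 + 0 = 2.
- No grade: 0 + 0 + 3 = 3.
- Total: 7 + 2 + 3 = 12.

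**5.3 notification (grades 2 to 5), all 12 profiles**

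- Covered: the four resolved profiles and the one unresolved profile that meets grade 3, so 4 + 1 = 5.
- Not covered: the three with grade 1 only and the three with no grade, so 3 + 3 = 6.
- Dependent on which grade the rater picks: 1 (grades 1 and 3).

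**The 6 incapacitating profiles (last two columns)**

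- Covered: 3 (grade 2; grades 2 and 3; grade 3).
- Not covered: 2 (grade 1 only; no grade).
- Dependent on the rater: 1.

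**5.1 against 5.3.** During the stay, 5.1 has the physician contacted for any adverse event, while 5.3 starts at grade 2. The two thresholds differ for every grade 1 event and every ungraded event on the ward. Staff can satisfy both by contacting the physician about everything. After discharge 5.1 no longer applies by its own terms, and 5.3 is the only rule that links an individual event's grade to physician notification.

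These are counts of logical cases, not expected frequencies. A coarser grouping of the attributes gives different counts. Merging incapacity with professional attention, for example, leaves 6 cells: 3 with one grade, 2 with two and 1 with none. Overlaps and a gap appear on either grouping.

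**The case against.** The strongest reply is that staff and other safeguards would handle these events sensibly.

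- **Grading on the ward.** A participant who is laid down and watched by nurses may well be receiving required professional medical attention, so grade 3 is available. The event might also be called disabling, a grade 4 term that the document does not define. This stands: a reader might infer that an observed incapacitating event must be graded Mild, and the text does not force that. But where both 1 and 3 apply, the scale gives no way to choose.
- **Need versus use of treatment.** A reader might infer that the scale measures how often staff gave treatment. Grade 1 speaks of treatment being required, which is a clinical judgement, and grades 3 to 5 use function or outcome. The defect lies in how grades 1 to 3 fit together.
- **Conflict between 5.1 and 5.3.** A reader might infer that the two rules cannot both hold. They can: 5.3 does not say that only grades 2 to 5 are notified, and the two sections differ in scope. What remains is a difference in threshold that the text leaves unexplained.
- **Other safeguards.** Besides 5.1, section 3.4.1(c) has the study physician evaluate participants before each discharge. Section 5.2.5 makes an event serious if it results in "A persistent or significant incapacity or substantial disruption of the ability to conduct normal life function", and 5.3 sends "All serious adverse events associated with the study procedures" to the ethics committee in writing within five working days. Questionable events are discussed weekly with the principal investigator. These cover much of the in-stay risk. They do not correct a recorded grade, a brief reaction may not count as serious, and weekly discussion may follow the next session, since 1.4.1 allows visits 48 hours apart.
- **No planned analysis.** A reader might infer that the comparison of cannabis, tobacco and the combination is biased. Section 6.3 lists dose, pharmacokinetic, heart rate, blood pressure and subjective variables, and adverse event grade is not among them. This objection stands in full.

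**Conclusion.** The concern holds as a defect in the grading definitions. Read literally, the scale gives exactly one grade to 7 of 12 profiles below grade 4, two grades to 2, and none to 3. An incapacitating event that needs no treatment can be graded Mild: that is its only grade if professional attention was not required, and one of two if it was. An event treated but not resolved that does not meet both grade 3 conditions has no grade. Such events can fall outside the notification rule in 5.3.

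The practical effect is limited. It lies mainly in the recorded severity, hence the descriptive safety record, and in events after discharge. The documents do not support saying that the physician would be unaware of an in-stay event, or that any prespecified comparison is affected.

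The conclusion assumes that staff apply 5.3 as written and that no grading manual outside these documents resolves the overlaps.

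**What to change.** 1. In 5.3, define grades 1 to 3 by effect on the participant's function alone, in ordered and mutually exclusive steps. State how inability to carry on normal activities differs from disabling in grade 4, and require exactly one grade per event. All six incapacitating profiles above would then share one grade, and no profile would be left without one.
2. Record treatment and outcome as separate items on the AE Form named in section 4. Its fields are not shown, so these items may already exist.
3. Reconcile the physician-notification statements in 5.1 and 5.3 so that it is clear which events are notified, during the stay and after discharge. Which threshold to use is for the investigators to decide. Settle it together with item 1: once treatment no longer sets the grade, a trivial event that resolved with treatment could move from grade 2 to grade 1, which 5.3 does not cover at present.

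The cost is a short amendment, which 8.4 requires to be approved before use, and a small change to adverse event recording for 14 participants. Nothing in the design, sampling schedule or analysis in 6.3 changes.

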5.4 PROTOCOL DEVIATIONS AND VIOLATIONS

Protocol deviations are defined as an event that deviates from the defined study protocol, but does not pose any risk to the participant or harm to the quality of the study data. For example, a follow-up call may be conducted outside of the stipulated window, or a section of questions on a questionnaire may be missed due to a mistake in branching. Deviations will be recorded on a protocol deviation sheet and reviewed and signed by the PI.

Protocol violations are events that deviate from the defined study protocol, but put the participant at risk and/or cause harm to the study data. For example, if a participant was enrolled in the study but they were under the age of 12 or they were enrolled without consent of a parent. Protocol violations will be recorded on a protocol violation sheet, reviewed and signed by the PI and reported to the CHR.

6 DATA COLLECTION AND MANAGEMENT

6.1 DATA COLLECTION FORMS

Data Collection Forms entered by participants include:

1. Screening packet, except Physiological Assessment Form
2. REDCap Questionnaire
3. Research Ward Outpatient Questionnaire Packets 1-10

Data Collection Forms entered by Research Staff:

1. Physiological Assessment Form of the Screening Packet
2. Outpatient Product Weight Record

6.2 DATA ENTRY, STORAGE, AND ANALYSIS

A folder “**XXXX ECig THC**” on the shared drive utilized by the Clinical Pharmacology Lab will be used to store electronic data from this study (where XXXX is the CTSI-CRS study number).

All databases are password protected with the following: **XXXXTHC**

1. Information collected from messages in the REDCap questionnaires will be entered by CRC in the **Call Log** database
2. A record of participants screened and/or enrolled is kept by CRC using the **Participant Log**
3. Personal data and Demographic data from the Screening Packet are entered by the CRC in the **Personal Data & Demographics database**
4. Information entered by the participant on the Screening Packet are entered in the **Screening Database** by the CRC
5. Data collected during the outpatient days, except questionnaire data, are entered by CRC in **Outpatient Measures**
6. Questionnaire data from the Inpatient days are entered by the CRC in **Outpatient Questionnaires**

6.3 DATA ANALYSIS

The study is not hypothesis-driven but will provide valuable data to guide future research as well as provide needed data on THC delivery and effects from vaping. Variables of interest include amount of THC inhaled, amount exhaled, and amount retained; pharmacokinetic parameters for THC, 11-OH-THC, and nicotine, the psychoactive compounds; heart rate and blood pressure change; and subjective effects.

Delivered and Retained Doses: Delivered THC and nicotine doses are estimated as the change in e-cigarette weight \times concentration of THC or nicotine in e-liquid. The amount of THC or nicotine systemically retained is estimated as delivered dose minus amount in gas traps.

THC, 11-OH-THC, and Nicotine Pharmacokinetics: Pharmacokinetic parameters will be estimated from blood THC and 11-OH-THC and plasma nicotine concentrations using Phoenix WinNonlin 6.3 (Pharsight Corporation, Mountain View, CA). Time to max concentration (T_{max}), max concentration (C_{max}), and area under the blood/plasma concentration-time curves (AUC) will be estimated using a non-compartmental model and trapezoidal rule. C_{max} , and $AUC_{0 \rightarrow \infty}$ will be adjusted for baseline nicotine levels.

Averages and 95% confidence intervals will be computed by e-liquid type (THC only or

THC+nicotine). Although this study is not hypothesis-driven, we will use mixed model analysis of variance (ANOVA) to assess differences in these variables between e-liquids type. Models will include sex as a covariate.

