1.3 SPECIFIC AIMS/OBJECTIVES

1. To characterize Δ^9 -tetrahydrocannabinol (THC) delivery, systemic exposure, and effects from vaping THC-containing cannabis leaf alone or cigarette tobacco alone, or the combination of cannabis and tobacco.
2. To assess sympathetic nervous system (SNS) stimulating and subjective SNS-related effects of THC alone compared to nicotine (tobacco) alone or combined to THC and nicotine co-administration.
3. To assess emissions of THC, terpenes, and other compounds from electronic THC delivery devices.

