1.4 STUDY DESIGN

1.4.1 Design Summary

The study is designed as a within-subjects single-blinded crossover study. Fourteen smokers of tobacco cigarettes and cannabis will switch between three conditions, namely: (a) vaping cannabis leaf, (b) vaping tobacco containing nicotine and (c) vaping a combination of cannabis leaf and tobacco containing nicotine. All participants will vape each product with the PAX loose-leaf vaporizer.

PAX vaporizers will be purchased by the study team. The cannabis leaf will be obtained through the National Institute on Drug Abuse Drug Supply Program. The tobacco containing nicotine, used in conditions (b) and (c) will come from commercially available Marlboro brand cigarettes. The same amount of cannabis or tobacco will be used in all conditions.

The study will be conducted during three outpatient visits separated by at least 48 hours. The order of treatment (cannabis leaf, tobacco with nicotine, cannabis leaf & tobacco with nicotine) will be counterbalanced between subjects. Subjects will be blinded to the content of the vaporizer on the study day but will be told during screening that they will vape cannabis alone, tobacco alone, and cannabis plus tobacco with nicotine.

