1.42 Number of Subjects

A total of 14 subjects will be enrolled in this study over a period of about 6 months. The anticipated accrual rate is approximately 2-4 subjects per month.

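### Section 6.3 compares nicotine only between cannabis alone and the combination; the informative contrast, tobacco alone against the combination, is not planned

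*Combined protocol and SAP*

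**What the plan says.** The design is a three-condition crossover. Section 1.4.1 states that "Fourteen smokers of tobacco cigarettes and cannabis will switch between three conditions". Section 1.42 gives the size: "A total of 14 subjects will be enrolled in this study". The conditions, abbreviated here to C, T and C+T, are set out in section 1.4.1 as "a) vaping cannabis leaf, (b) vaping tobacco containing nicotine and (c) vaping a combination of cannabis leaf and tobacco containing nicotine". Aim 1 in section 1.3 covers "vaping THC-containing cannabis leaf alone or cigarette tobacco alone, or the combination of cannabis and tobacco".

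Section 6.3 lists the variables of interest: THC inhaled, exhaled and retained; "pharmacokinetic parameters for THC, 11-OH-THC, and nicotine, the psychoactive compounds"; heart rate and blood pressure change; and subjective effects. It also gives a formula for delivered and retained nicotine dose. On summaries it says "Averages and 95% confidence intervals will be computed by e-liquid type (THC only or", and the parenthesis closes with THC plus nicotine as the second and last type. On comparisons it says that "we will use mixed model analysis of variance (ANOVA) to assess differences in these variables between e-liquids type". The only other feature of the model is "Models will include sex as a covariate". It does not say which conditions enter for which variable, and it gives no covariance structure.

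The blood table in section 3.4.3 has a nicotine/cotinine tube and a THC tube at all 11 times on all three study days.

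**The concern.** One two-level factor is applied to every variable, but the two drugs are not present in the same conditions. C and C+T both contain THC, so the factor fits THC and 11-OH-THC. For nicotine, the two conditions that contain it are T and C+T, and T is not a level.

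Followed literally, the plan reports nicotine dose, Cmax, AUC and Tmax as a comparison of no nicotine with some nicotine. It yields no estimate of how nicotine exposure differs between vaping tobacco alone and vaping it with cannabis. It does not even plan a nicotine average and interval for tobacco alone. The data for both would be collected and left out of the planned analysis.

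**Working it through.** The documents state no effect size, SD or correlation, so there is no figure of the plan's own to reproduce. The CVs and correlations below are assumptions, shown over a range.

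**1. Which conditions contain which drug (sections 1.4.1 and 1.6.2)**

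| Variable | C | T | C+T | Pair in 6.3 | Informative pair |
|---|---|---|---|---|---|
| THC, 11-OH-THC | given | not given | given | C, C+T | C, C+T |
| Nicotine | not given | given | given | C, C+T | T, C+T |

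The pairs agree for THC and differ for nicotine.

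**2. What nicotine looks like in C.** Section 6.3 takes delivered dose as device weight change × concentration. The nicotine concentration of cannabis leaf is 0, so the dose is exactly 0 whatever the weight change. Cmax and AUC are adjusted for baseline nicotine, which leaves values near 0. Tmax has no absorption peak from the session to locate.

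**3. How empty the planned nicotine test is.** Take C as 0 and C+T as mean 1 with between-person SD equal to the CV. The paired t statistic is then centred near √14/CV, on 13 df (two-sided 5% critical value about 2.16).

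| Assumed CV | √14/CV | Rejection rate (20,000 simulated trials) |
|---|---|---|
| 0.5 | 7.48 | 100% |
| 0.8 | 4.68 | 99% |
| 1.0 | 3.74 | 93% |

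Nothing about the effect of cannabis on nicotine uptake enters this calculation.

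**4. Why adding T as a third level is not enough for drug levels.** Suppose all three conditions enter a random-intercept model with one pooled residual. Let the two conditions containing the drug have variance 1 and within-person correlation ρ, and let the third be 0.

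- Contrast between the two active conditions, divided by √2: variance 1 − ρ. This is the correct error.
- Sum of the two active conditions minus twice the zero condition, divided by √6: variance (2 + 2ρ)/6 = (1 + ρ)/3.
- The pooled residual is the average: [(1 − ρ) + (1 + ρ)/3]/2 = (2 − ρ)/3.
- Ratio of the SE used to the correct SE: √[(2 − ρ)/(3(1 − ρ))].

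| ρ (assumed) | SE ratio | Coverage of nominal 95% interval, pooled, 26 df |
|---|---|---|
| 0 | 0.82 | 89.1% |
| 0.3 | 0.90 | 92.3% |
| 0.5 | 1.00 | 94.9% |
| 0.7 | 1.20 | 98.0% |
| 0.9 | 1.91 | 99.9% |

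The two-condition paired analysis covers 94.8 to 95.2% at every ρ tried. Giving the zero condition a small residual SD (0.1 of the active SD) changes the pooled coverage by at most 0.003. With no true difference between the two active conditions, the three-level omnibus test still rejects in 96 to 100% of trials (CV 0.5 to 1.0).

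**5. Error degrees of freedom.** Two conditions: (14 − 1)(2 − 1) = 13. Three conditions: (14 − 1)(3 − 1) = 26.

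**The case against.** The best defence is that 6.3 carries over e-cigarette wording, that the study disclaims formal hypotheses, and that any analyst would see that nicotine should be compared between T and C+T. Aim 1 also names THC, not nicotine, as the exposure to be characterised, and the THC comparison is intact. Much of this stands: the cause is an incomplete factor, and the THC results do not suffer. But 6.3 itself lists nicotine pharmacokinetics as a variable of interest and commits to intervals and a comparison by the types it names. Being descriptive does not make an uninformative contrast useful.

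Three stronger readings are tempting, and the documents do not support them.

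- A reader might infer that the THC analyses are distorted by tobacco-only sessions without THC. Section 6.3 does not name T as a level, so none enter.
- A reader might infer that the planned intervals have wrong coverage. The coverage table applies only if all three conditions enter a model with one pooled residual, which 6.3 neither specifies nor excludes. The error could also go either way. A crossover is usually chosen because within-person correlation is expected, so the row at ρ = 0 is the least relevant. Averages and intervals computed within each condition are unaffected.
- A reader might take THC in T to be zero after baseline adjustment. Section 6.3 adjusts only for nicotine, and section 1.5.1 requires THC-positive regular users who abstain for 12 hours, so measured THC may be low rather than absent.

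**Conclusion.** The point holds for nicotine. Read literally, 6.3 plans an uninformative nicotine comparison (C against C+T) and omits the informative one (T against C+T). That conclusion needs no variance assumption: it follows from the conditions and from the two types named. It does rest on reading the types in the sentence on averages as the levels of the ANOVA in the sentence after it; the section offers no others. The rejection rates of 93 to 100% only illustrate how little the planned test can tell, and they depend on the assumed CVs.

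The THC and 11-OH-THC comparison should stay as it is. The SE and coverage figures are a caution about one way of rewriting the section, not a fault in the present text: too narrow below a within-person correlation of 0.5, about right at 0.5, too wide above. The correlation is unknown.

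**What to change.** In section 6.3, state the conditions for each group of variables:

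- Nicotine dose, Cmax, AUC and Tmax: T and C+T sessions only.
- THC dose variables, and THC and 11-OH-THC pharmacokinetics: C and C+T sessions only.
- Heart rate, blood pressure change and subjective effects: all three conditions.
- Nicotine in C and THC in T: descriptive only, as checks on abstinence and carry-over.

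Use the same sets for the averages and 95% intervals. For the drug-level variables, do not simply extend the factor to three levels with one pooled residual, for the reason in step 4.

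The cost is a few sentences of text, with no new samples or participants. The pharmacokinetic contrasts have 13 error degrees of freedom instead of the 26 of a three-condition model. The two-level comparison now in 6.3 also has 13, so nothing is lost against the present plan.
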